### 6.2.3.9.3 Percent of patients with improvement of EORTC-QLQ-PR25 urinary symptoms

Patients will be defined as having EORTC-QLQ-PR25 urinary improvement, if they experience a decrease of  $\geq 8$  points in EORTC-QLQ-PR25 urinary symptoms score, scale (PRURI), from baseline.

Improvement from baseline in EORTC-QLQ-PR25 urinary symptoms score will be compared between treatment arms using a Cochran-Mantel-Haenszel test stratified by stratification factor of PSADT ( $\leq 6$  vs.  $>6$  months) and use of osteoclast-targeted therapy (yes vs. no) at randomization.

### 6.2.3.9.4 Time to worsening of EORTC-QLQ-PR25 urinary symptom score

A patient's time to worsening of EORTC-QLQ-PR25 urinary symptoms will be defined as the time from randomization to the deterioration date. For patients with no symptomatic deterioration at the time of the analysis, the time to deterioration will be censored at the date of the last EORTC-QLQ-PR25 (PRURI) valid assessment.

Patients will be defined as having EORTC-QLQ-PR25 urinary symptoms deterioration if they experience an increase of greater or equal to 8 points in EORTC-QLQ-PR25 urinary symptoms score, scale (PRURI), from baseline.

Table 21 will be used for calculating the time to worsening of EORTC-QLQ-PR25 urinary symptoms. Time to worsening of EORTC-QLQ-PR25 urinary symptoms = End Date - Date of randomization +1.

**Table 21: Censoring Rules for time to worsening of EORTC-QLQ-PR25 urinary symptoms**

Situation	End Date on or prior to cut-off date	Censored
No baseline or post-baseline EORTC-QLQ-PR25 urinary assessment	Date of randomization	Yes
No worsening in EORTC-QLQ-PR25 urinary symptoms score	Last EORTC-QLQ-PR25 urinary symptoms assessment date	Yes
Patient had a worsening in EORTC-QLQ-PR25 urinary symptoms	The date of first observation of worsening in EORTC-QLQ-PR25 urinary symptoms	No

This endpoint is selected from the ADTTE dataset using variable PARAMCD equal to 'EORTCWOR'.

Times to worsening will be displayed by the product-limit estimates of the survival distribution functions (Kaplan-Meier) for each treatment group: N, total censored, total failed, survival time (median and its 95% CI, range), deterioration-free rate at 12, 24, and 36 etc.... months, KM curves. The hazard ratio darolutamide over placebo, its 95% CI will be generated from the Cox model.

#### 6.2.3.9.5 Percent of patients with deterioration of EQ-5D-3L utility score at 16 weeks

Patients will be defined as having a deterioration in EQ-5D-3L index if they experience a deterioration of greater or equal 0.06 points compared to baseline at 16 weeks after start of treatment.

Deterioration from baseline in EQ-5D-3L index score will be compared between treatment arms using a Cochran-Mantel-Haenszel test stratified by stratification factor of PSADT ( $\leq 6$  vs.  $>6$  months) and use of osteoclast-targeted therapy (yes vs. no) at randomization.

Analysis will be created on both sub-sets of patients:

- FAS,
- FAS excluding patients with no visit at week 16.

#### 6.2.4 Subgroup analysis

There are specific subgroup analyses of interest which will be performed for the primary endpoint (MFS) and the secondary endpoints (OS).

Subgroup analyses will be based on FAS analysis set.

Descriptive statistics and hazard ratio with 95% CI will be provided within each category, provided there are a sufficient number of patients in total within the subgroup across the treatment arms. All subgroups analyses will be done on non-stratified Cox model and log-rank test.

Subgroup analyses of interest:

- Baseline CRF PSADT ( $\leq 6$  and  $>6$  months),
- Baseline CRF osteoclast-targeted therapy (yes vs. no),
- Baseline PSA (ng/mL) ( $\leq 10$ ;  $>10$  to  $\leq 20$ ;  $>20$ ) from central laboratory,
- Baseline PSA (ng/mL) (at or below median vs. above the median [median of all patients]) from central laboratory,
- Gleason score at diagnosis ( $\geq 7$  vs.  $<7$ ),

- Age (years) (<65, 65- 74, 75 - 84, ≥85),
- Geographical region (North America, Asia Pacific, ROW),
- Baseline presence of regional pathological lymph nodes (yes vs. no) by central imaging review,
- Baseline ECOG performance status (0, 1),
- Race: White, Asian, Black or African American, Other; ethnicity ‘Hispanic or Latino’ will be shown as well as it cannot be mapped to the Bayer race subgroups,
- Number of prior hormonal therapies (1, ≥2) (for definition of hormonal therapies, refers to Section 9.13).

Further important baseline cancer characteristics may also be considered.

Subgroup analyses will not be performed for the sensitivity analyses.

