7.4 General statistical considerations

Statistical analysis will be performed using the datasets defined above.

Primary efficacy will be evaluated at the end of double-blind part when targeted number of primary endpoint events is collected.

To determine whether demographic or baseline characteristics influence the response to treatment, subgroup analyses will be performed on the efficacy variables by the treatment and the relevant subgroup variable in question e.g., disease characteristics and previous therapies. Subgroups will be specified in the SAP. The stratification factors PSADT and use of

osteoclast-targeted therapy at randomisation will be used to adjust primary and all secondary efficacy analyses.

Incomplete event occurrence dates will be imputed as the earliest possible date. Missing event dates e.g., due to withdrawal of consent, lost to follow up or not known to have died at the analysis cut-off date, will be right censored. Detailed methods will be described in the SAP.

All efficacy and safety data will be tabulated using appropriate descriptive statistics. Detailed description of all statistical methods will be defined in the SAP.

Data from patients who are transferred to a roll-over study may be pooled and analyzed together with the data from the study in which the patient was initially included. The results from these analyses will be reported separately.

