### **3.1 Determination of Sample Size**

Several clinical publications were used as basis for the sample size calculation. The median MFS for placebo is based on denosumab phase III study results [8] at the time the ARAMIS protocol was designed, no data were available on the expected treatment effect size for androgen-receptor inhibitors in high-risk nmCRPC patients. Data published in 2016 and recently published data from SPARTAN and PROSPER phase III trials indicate, that the treatment effect of the class of novel androgen receptor inhibitors (enzalutamide, apalutamide) is stronger than initially assumed

Given the results from PROSPER and SPARTAN, the initial assumption for the treatment effect size of a hazard ratio of 0.75 was considered as too conservative.

All patients had to have an independent evaluation of radiological images for no baseline metastases at baseline to be eligible for randomization. However, for the central efficacy review, the baseline scans were again reviewed. During this review some patients were identified with metastases at baseline; to calculate sample size these patients are considered as having a MFS event on the date of randomization.

The number of events has been adjusted to account for the non-informative character of baseline metastases events and the dilution impact to the estimated MFS hazard ratio.

The assumptions used in determining the sample size for this study are as follows:

- Overall 2-sided type I error rate: 0.05,
- Assumed hazard ratio of 0.65,

- Accounting for 5% of the patients with baseline metastasis, diluted hazard ratio of 0.71,
- Randomization ratio: 2:1
- Statistical power at the final analysis: 91%,
- Median MFS for placebo: 25 months,

385 MFS events will provide approximately 91% power to detect a statistically significant difference in MFS times, with a two-sided log-rank test with a 0.05 level of significance. With 40 months accrual time and a dropout rate of 40%, the study will require approximately 1500 patients (1000 darolutamide patients, 500 placebo patients) to achieve the targeted 385 MFS events. The MFS analysis will be performed when the targeted number of approximately 385 MFS events has been observed.

This sample size calculation was performed with a simulation based algorithm.

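### The subgroup analyses are meant to show whether baseline characteristics influence the response to treatment, but the SAP plans only within-category estimates and tests and no treatment-by-subgroup test

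*SAP*

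**What the plan says.** Protocol 7.4 gives the purpose: "To determine whether demographic or baseline characteristics influence the response to treatment, subgroup analyses will be performed on the efficacy variables". The sentence goes on to say that this is done by treatment and subgroup variable, and the section leaves the choice of subgroups and the detailed methods to the SAP.

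SAP v4.2, 6.2.4 applies the subgroup analyses to MFS and OS in the FAS. It lists 11 factors, including two codings of baseline PSA, and shows Hispanic or Latino ethnicity alongside race. On output it says "Descriptive statistics and hazard ratio with 95% CI will be provided within each category", provided the subgroup has enough patients. On method it says "All subgroups analyses will be done on non-stratified Cox model and log-rank test".

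Neither document mentions an interaction term, a heterogeneity test, a ratio of hazard ratios or any rule for comparing categories. SAP 6.2.4 does not label the subgroup results exploratory, although SAP 6.4 does so for biomarkers and SAP 6.2.3 calls the tertiary-endpoint p-values informative only.

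**The concern.** The protocol's question concerns a difference between categories. Its null hypothesis is that the treatment effect is the same in all categories of a factor. A log-rank test inside one category has a different null, namely no effect in that category.

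Each category holds only part of the events. With one common true effect, some categories can therefore reach p<0.05 and others not, simply because power differs or chance intervenes. Someone looking for effect modification may then read a significant category beside a non-significant one as evidence that some men do not benefit. Conversely, a real difference in effect has no test aimed at it.

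**Working it through.** **Inputs from SAP 3.1.** 385 MFS events; 2:1 allocation; a two-sided 5% significance level; a hazard ratio of 0.65 before dilution; for the diluted value, "Accounting for 5% of the patients with baseline metastasis, diluted hazard ratio of 0.71"; stated power about 91%, obtained by simulation. SAP 6.2.2 gives about 240 OS events at the final test, with 140 at the interim as an example.

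**Assumptions.** The documents give no category sizes. The only split fixed by definition is baseline PSA at or below versus above the median, which halves the patients; I assume that it also halves the events. The documents give no OS hazard ratio, so I use 0.71 to 0.80.

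**The plan's own figure.** Freedman's formula for 2:1 gives power = Φ(√(2 × 385) × (1 − 0.71)/(1 + 2 × 0.71) − 1.96) = Φ(1.365) = 91.4%, which agrees with the SAP. Schoenfeld's formula for 2:1 gives 88.6%. Because the SAP used simulation, this gap is not an error in the plan. I use Schoenfeld below and show Freedman as a check.

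**Two categories with the same true hazard ratio.** The power in a category with d events is Φ(√(d × 2/9) × |ln HR| − 1.96). If the two powers are p₁ and p₂, exactly one category is significant with probability p₁(1 − p₂) + p₂(1 − p₁).

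- HR 0.71, 192.5 events each: Φ(6.54 × 0.342 − 1.96) = Φ(0.28) = 61.0%; 2 × 0.610 × 0.390 = **47.6%**.
- HR 0.65, 192.5 events each: Φ(6.54 × 0.431 − 1.96) = 80.4%; 2 × 0.804 × 0.196 = **31.5%**.
- HR 0.65, 310 events in total: this assumes that baseline-metastasis events are left out, 385 − 5% × 1500 = 310. Power is 71.5% in each half; 2 × 0.715 × 0.285 = **40.7%**. The 310 is consistent with the SAP's dilution, since exp(ln 0.65 × 310/385) = 0.707.

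Uneven event splits raise the figure:

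| MFS case | 50:50 | 70:30 | 90:10 |
|---|---|---|---|
| HR 0.71, 385 events | 47.6% | 54.5% | 73.3% |
| HR 0.65, 385 events | 31.5% | 42.7% | 74.0% |
| HR 0.65, 310 events | 40.7% | 50.0% | 75.1% |

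Freedman's formula gives 45.4% for equal halves at 0.71 and 25.8% at 0.65. With three or four equal categories, the chance that they do not all agree is 74% or 81% at 0.71, and 70% or 87% at 0.65.

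For OS, over splits from 50:50 to 90:10, the range is 33% to 62% at 240 deaths and 24% to 45% at 140. With no effect anywhere it is 2 × 0.05 × 0.95 = 9.5%.

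**An interaction test on the same data.** Under a common effect it rejects in 5% per factor (simulated 5.0%). For equal halves of 385 events, the SE of the log ratio of hazard ratios is √(2/(192.5 × 2/9)) = 0.216.

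- Ratio 0.71: power Φ(0.342/0.216 − 1.96) = 35% (31% for a 70:30 split).
- Ratio 0.50, for example HR 0.50 versus 1.00: power Φ(0.693/0.216 − 1.96) = 89%.
- A ratio of about 0.55 is needed for 80% power.
- Eleven factors treated as independent: 1 − 0.95¹¹ = 43% chance of at least one false interaction per endpoint.

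**The case against.** Four points on the other side have weight.

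First, the information is not lost. Categories of one factor are disjoint, so the log ratio is ln HR₁ − ln HR₂ with SE √(SE₁² + SE₂²), and each SE can be recovered from the planned CI. A reader might infer that the planned analyses cannot answer the protocol's question. That goes too far: what is missing is a planned and reported comparison, not the data for one.

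Second, a reader might infer that categories will look different about half the time, or that a uniform benefit will usually appear as present here and absent there. The documents support neither. The 48% is the chance that one p-value is below 0.05 and the other is not; it does not describe the hazard ratios and CIs, which the SAP also reports. It belongs to HR 0.71 with equal halves. Across other plausible inputs the range runs from about a quarter to over 80%, and for the median-PSA split under equal events every case shown is below half. Nor does either document say that significance in one category will be set against non-significance in another.

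Third, the remedy is weak for modest differences, as the 35% and 43% figures show.

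Fourth, the subgroup analyses carry no alpha and no decision rule, so the confirmatory tests are not touched.

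All four stand, and they limit the point. They do not remove it: the protocol asks about influence on response, the SAP plans tests of something else, and the subgroup section carries no exploratory label.

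**Conclusion.** The point holds as a mismatch between the stated purpose and the planned method. SAP 6.2.4 should include a direct comparison of treatment effects between categories, and it does not.

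Under a uniform MFS effect, two equal categories would disagree on significance in about 48% of trials at HR 0.71 and 31% at 0.65, or 41% at 0.65 with 310 events, against 5% per factor for an interaction test. These figures rest on an assumed equal split of events, normal approximations and, for the 310, the assumption that baseline-metastasis events are excluded. The OS figures also rest on an assumed hazard ratio. The conclusion does not depend on any single figure: wherever a real common effect was assumed, the disagreement rate was at least 24%.

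The consequence is for interpretation of the subgroup results only. The primary MFS test, its type I error and the secondary-endpoint hierarchy are unaffected.

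**What to change.** In SAP 6.2.4, for each of the 11 factors and for both MFS and OS:

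- Fit one Cox model on the FAS with treatment, subgroup and treatment-by-subgroup terms. Stratifying this model by the randomisation factors is optional.
- For two-category factors, report the ratio of hazard ratios with 95% CI and the interaction p-value. For factors with more categories, give a global heterogeneity test.
- Label these results exploratory and unadjusted for multiplicity, and note the low power and the familywise figure.
- Keep the within-category hazard ratios and 95% CIs. Drop the within-category log-rank p-values, or give them less prominence.

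The cost is a few lines of SAP text and one extra model per factor and endpoint. The drawback is that a non-significant interaction will not show that the effect is uniform: power is only about 35% for a ratio of 0.71 even in equal halves. Some false signals are also to be expected across 11 factors. The 43% is approximate, because the factors are not truly independent; two of them are codings of the same PSA value.

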### 6.3 Pharmacokinetics/pharmacodynamics

PK sampling will be undertaken at centers participating in PK sample collection. It is estimated that approximately 600 patients will participate in the PK sampling, resulting in approximately 400 patients randomized to receive darolutamide being included in the population PK analysis.

Venous blood samples will be collected for determination of darolutamide, the diastereomers (*S,R*)-darolutamide and (*S,S*)-darolutamide and the metabolite keto-darolutamide concentrations in plasma.

Pharmacokinetics of darolutamide: PK data will be analyzed using a population PK model to explore possible relationships between selected demographics and clinical covariates and drug/metabolite exposure.

Pharmacokinetic analyses and results will be provided in a separate report. Full details of the modelling will be provided in a separate Modelling & simulation analysis plan.

### 6.4 Biomarker evaluation

Blood (plasma) samples will be collected for tumour-related biomarker assessments and a whole blood sample for pharmacogenetic (PG) assessments. Patients’ biomarker status will be correlated with clinical treatment effect to explore which targets may be important in defining the appropriate therapeutic population for the agent.

Since this clinical study is not powered to specifically address biomarker questions, and since the analysis will be conducted retrospectively, these biomarker analyses are considered exploratory.

Biomarker analyses and results will be provided in a separate report.

## 6.5 Safety

No formal statistical tests will be done for the safety endpoints. All analyses for safety will be performed in the SAF population.

An updated analysis of safety events will be performed as of the final OS analysis.

Specific tables of adverse events will be displayed by following subgroups:

- Age (years) :<65, 65 - 74, 75 - 84, ≥85,
- Geographical region (North America, Asia Pacific, ROW).
- Renal function - eGFR at baseline (normal vs.mildly impaired vs. moderately impaired, severely impaired and end stage renal disease) (for calculation see Section 6.1.2),
- Hepatic impairment at baseline (normal vs mild vs moderate and severe impairment) (for calculation see section 6.1.2),
- Concomitant statin use (no vs. yes), to be determined by concomitant medication (see Appendix 9.9).

### 6.5.1 Extent of exposure

Extent of exposure will be summarized for the SAF by treatment group, using descriptive statistics.

Duration of study treatment will be calculated in days and presented in months as the date of the last dose of any study treatment – date of the first dose of any study treatment + 1.

Dose modification will be summarized.

Extent of exposure will be described by age groups and geographical regions.

### 6.5.2 Adverse events

All adverse events (AE) whether considered drug-related or not, will be reported on the CRF with diagnosis, start/stop dates, dates of any grade change, action taken, whether treatment was discontinued, any corrective measures taken, and outcome. For all events, the relationship to treatment and the severity of the event will be determined by the Investigator. AEs will be classified and coded using the National Cancer Institute (NCI) Common Terminology Criteria Adverse Event (CTCAE), version 4.03.

The treatment period for this study, for purposes of safety analyses, extends from the initiation of study treatment until 30 days after the last administration of study treatment.

Each change in AE grade was entered as a separate record with no automatic link to the original AE record, which may lead to variations of the verbatim for the same AE. This makes a correct grouping of AE grades, which actually belong together, not always possible. An AE is considered as treatment-emergent (TEAE) if there is an AE record which starts during treatment or within the post-treatment time window of 30 days.

For further definitions of the terms AE, SAE, seriousness, intensity, causal relationship with treatment, causal relationship to protocol-required procedures, action taken, and outcome; see Protocol Section 6.6.1.

Descriptive summary tables (frequency and percentage of patients, not of events) will be presented by treatment group and MedDRA version 20.0, or the most recent version terminology, for the following:

- AEs during screening
- Treatment-emergent AEs
- Treatment-emergent AEs with grade 3, 4, or 5
- Treatment-emergent AEs occurring in at least 1% of patients
- Treatment-emergent AEs occurring in at least 5% of patients
- Treatment-emergent AEs leading to study drug withdrawal
- Treatment-emergent AEs leading to dose reduction
- Treatment-emergent AEs leading to drug interruption
- Treatment-emergent AEs leading to dose reduction and/or drug interruption
- Treatment-emergent drug-related AEs
- Treatment-emergent drug-related AEs with grades 3, 4, or 5
- Treatment-emergent drug-related AEs occurring in at least 5% of patients in any treatment arm
- Treatment-emergent drug-related AEs leading to study drug withdrawal
- Treatment-emergent drug-related AEs leading to dose reduction
- Treatment-emergent drug-related AEs leading to drug interruption
- Treatment-emergent drug-related AEs leading to dose reduction and/or drug interruption

Interval specific and cumulative event rates for treatment-emergent adverse events (for AE with at least a 5% total incidence rate (any grade)).

Subgroup analyses will be performed for TEAEs. Tables showing differences of at least 5% points in incidence proportions between any of the subgroup categories will be produced.

Following treatment-emergent adverse events are considered as special topics:

- Bone fracture (selected using HLT: Fractures and dislocations NEC (without PTs: Joint dislocation, Joint dislocation pathological), Limb fractures and dislocations (without PT: Radial head dislocation), Pelvic fractures and dislocations, Skull fractures, facial bone fractures and dislocations, Spinal fractures and dislocations (without PT: Dislocation of vertebra), Thoracic cage fractures and dislocations (without PT: Dislocation of sternum))
- Fall (selection of MLG Fall (only PT Fall))
- Seizure (selection of MLG Seizures)
- Fatigue (selection of MLG decreased general strength and energy, selection of PT Lethargy, Malaise, Chronic fatigue syndrome)
- Weight decreased (selection of MLG Weight decreased)

Following tables will be created for the TEAE of special topics

- Treatment-emergent AEs
- Treatment-emergent AEs leading to study drug withdrawal
- Treatment-emergent AEs leading to dose reduction
- Treatment-emergent AEs leading to drug interruption
- Treatment-emergent SAEs

Incidence of TEAEs of special topics will be displayed for the subgroup of concomitant statin use.

Fracture events will be described by a cumulative incidence plot of fracture. A summary of treatment-emergent fracture by bone sparing agent use (for selection of bone sparing agent see Appendix 9.14) at study entry will be provided. Association with weight decrease will be presented by histogram of fracture events by patient weight change (the weight collected closest to the start of fracture will be considered and compared to baseline weight).

A listing will be generated for patients with fall treatment-emergent events with syncope and/or loss of consciousness (using the MLG Syncope).

An overview of patients at risk for developing an AE seizure will be tabulated by displaying medical history.

Listing of non-treatment-emergent AEs will be created.

Incidence of post treatment non-treatment-emergent AEs will be tabulated.

To adjust for unequal lengths of study treatment period among patients, and potentially between treatment groups, an additional summary based on event rate per 100 patient year will be performed for all AEs, special topics AEs and all SAEs occurring after the first dose

of study treatment. The event rate per patient is calculated as the total number of events divided by the total treatment duration in years.

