7.8.1 Evaluation of adverse events

AEs will be summarised. Treatment emergent AEs are defined as AEs with an onset date on or after the first dose of study treatment and up to the end-of-study treatment visit. For all AEs, CTCAE v4.03 terminology should be recorded in the appropriate section of the AE CRF. All AEs will be coded using the Medical Dictionary for Regulatory Activities (MedDRA) coding system. The incidence of AEs will be presented by MedDRA system organ class and preferred term, relationship to study drug treatment, and severity. A patient reporting the same AE more than once is counted only once when evaluating incidence, maximum severity or strongest relationship to study treatment. To adjust for unequal lengths of study treatment period among patients, and potentially between treatment groups, an additional summary based on event rate per patient year will be performed for all AEs and all SAEs occurring after the first dose of study treatment.

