## 6.5 Safety

All data including the open-label period will be summarized.

For patients randomized to darolutamide, safety events will be displayed separately for:

- the double-blind period

- the double-blind and open-label periods (total)

For patients randomized to placebo, safety events will be displayed separately for:

- the double-blind period
- the open-label period after cross-over to darolutamide treatment

The double-blind period of the study only will be considered for risk difference, risk ratio, interval-specific incidence and prevalence.

If the start date of the AE is missing then the event will be considered occurring during the double-blind period.

No formal statistical tests will be done for the safety endpoints. All analyses for safety will be performed in the SAF population.

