### **6.5.2 Adverse events**

All adverse events (AE) whether considered drug-related or not, will be reported on the case report form (CRF) with diagnosis, start/stop dates, dates of any grade change, action taken, whether treatment was discontinued, any corrective measures taken, and outcome. For all events, the relationship to treatment and the severity of the event will be determined by the Investigator. AEs will be classified and coded using the National Cancer Institute (NCI) Common Terminology Criteria Adverse Event (CTCAE), version 4.03.

The treatment period for this study, for purposes of safety analyses, extends from the initiation of study treatment until 30 days after the last administration of study treatment.

Each change in AE grade was entered as a separate record with no automatic link to the original AE record, which may lead to variations of the verbatim for the same AE. This makes a correct grouping of AE grades, which actually belong together, not always possible. An AE is considered as treatment-emergent (TEAE) if there is an AE record which starts during treatment or within the post-treatment time window of 30 days.

For further definitions of the terms AE, SAE, seriousness, intensity, causal relationship with treatment, causal relationship to protocol-required procedures, action taken, and outcome; see Protocol Section 6.6.1.

Descriptive summary tables (frequency and percentage of patients, not of events) will be presented by treatment group and MedDRA version 24.0, or the most recent version for the following:

- Pre-treatment AEs
- TEAEs
- TEAEs with grade 3, 4, or 5
- TEAEs occurring in at least 1% of patients
- TEAEs occurring in at least 5% of patients
- TEAEs leading to study drug withdrawal
- TEAEs leading to dose reduction
- TEAEs leading to drug interruption
- TEAEs leading to dose reduction and/or drug interruption
- Drug-related TEAEs
- Drug-related TEAEs with grades 3, 4, or 5
- Drug-related TEAEs occurring in at least 5% of patients in any treatment group
- Drug-related TEAEs leading to study drug withdrawal
- Drug-related TEAEs leading to dose reduction
- Drug-related TEAEs leading to drug interruption
- Drug-related TEAEs leading to dose reduction and/or drug interruption
- Interval specific and cumulative event rates for TEAEs (for TEAEs with at least a 5% total incidence rate (any grade)).
- Post-treatment non-treatment-emergent AEs

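### The record-based TEAE rule lets an adverse event that began before first dose and only improves on treatment count as treatment-emergent, contrary to the protocol; assignment of events ongoing at crossover is left open

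*SAP*

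**What the plan says.** SAP v4.2 section 6.5.2 describes how the data were captured: "Each change in AE grade was entered as a separate record with no automatic link to the original AE record". It concedes the consequence: "This makes a correct grouping of AE grades, which actually belong together, not always possible". It then defines treatment emergence at record level: "An AE is considered as treatment-emergent (TEAE) if there is an AE record which starts during treatment or within the post-treatment time window", the window being 30 days. Supplement 7 section 6.5.2 repeats these statements for the report that includes open-label data.

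Supplement 7 section 6.5 displays the events of men randomised to placebo separately for the double-blind period and for "the open-label period after cross-over to darolutamide treatment". Its only rule on assigning adverse events to a period covers missing dates: "If the start date of the AE is missing then the event will be considered occurring during the double-blind period".

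Protocol section 7.8.1 uses a different criterion: "Treatment emergent AEs are defined as AEs with an onset date on or after the first dose of study treatment".

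**The concern.** A TEAE table should show what is new or worse after treatment starts. Under the SAP rule one record starting on treatment is enough, and a fall in grade creates such a record. An older event that is resolving is then reported as if it had emerged.

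The SAP does not say that it departs from the protocol here. By contrast, its section 5 openly announces the decision to drop the per-protocol set, and its section 7 on changes lists only version dates.

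The double-blind TEAE tables could therefore include some events that predate treatment. The crossover column, which is the plan's display of men starting darolutamide after placebo, could include placebo-onset events. It has no concurrent control that would reveal the carry-over.

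**Working it through.** The plan states no figure to reproduce; this is a classification rule. The check applies three rules to constructed histories, then shows the arithmetic of carry-over under assumed shares.

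**Rules compared**
- SAP: any record starts in the window.
- Protocol: the event's onset falls in the window.
- New-or-worse: the event is new in the period, or its grade exceeds the last grade before the period's first dose.

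**Constructed histories** (first dose day 1; crossover day 400)

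| History | SAP | Protocol onset | New-or-worse |
|---|---|---|---|
| A: grade 2 on day -5, grade 1 on day 10 | TEAE | not a TEAE | not a TEAE |
| B: on placebo, grade 3 on day 380; grade 1 on day 415. Shown in crossover column? | yes, if periods follow record start | no | no |
| C: grade 2 on day -5, unchanged | not a TEAE | not a TEAE | not a TEAE |
| D: grade 2 on day 50, grade 3 on day 60, grade 1 on day 80 | TEAE | TEAE | TEAE |
| E: grade 1 on day -5, grade 3 on day 10 | TEAE | not a TEAE | TEAE |

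History A is the direct conflict between SAP and protocol. History E shows that simply reverting to the protocol wording would lose a genuine worsening. History B is already a TEAE overall under all three rules, because it began during placebo treatment; only the period in which it is displayed is in question. History D shows that an event that starts and then improves within one period adds no patient to a patient-based table.

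**Effect on incidence (illustration; every input is an assumption)**

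Let p be the true incidence of new events and c the share of otherwise event-free men whose older event only changes grade. Observed incidence = p + (1 - p) × c.

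Double-blind, assuming p = 10% against 5% (risk ratio 2.00) and the same c in both arms:
- c = 1%: 0.10 + 0.90 × 0.01 = 10.9%; 0.05 + 0.95 × 0.01 = 5.95%; ratio 1.83.
- c = 2%: 11.8% against 6.9%; ratio 1.71.
- c = 5%: 14.5% against 9.75%; ratio 1.49.

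Crossover column, assuming p = 10% and that records follow their own start dates: c = 1%, 2%, 5% and 10% give 10.9%, 11.8%, 14.5% and 19.0%.

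**What limits c in the double-blind part.** Protocol section 6.1.1 places screening within 28 days before first dosing. Protocol section 6.6.1.1.1 treats conditions that predate consent and have not changed as medical history. The pool is therefore events arising or deteriorating between consent and first dose, and then only those that change grade later. This points to the low end of the range above, but the documents give no rate with which to confirm it.

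**The case against.** **The crossover part is not what the text says.** Supplement 7 section 6.5 refers to the start date of the adverse event, not of a record. Assigned by event start, a placebo-onset event stays in the double-blind column. This stands. A reader might infer that placebo-onset events will be reported as darolutamide TEAEs, but the documents do not establish it. They give no rule for events ongoing at the switch, and with unlinked records the start date of the event is itself ambiguous.

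**Unseen documents may supply the rule.** SAP v4.2 section 4.3 refers the derivation of treatment emergence and periods to data management programming, an operational manual and standard guidelines. Supplement 7 also builds on Supplement 4. None of these was available, so a worsening or period rule may exist there. It would still need to be squared with the explicit rule in section 6.5.2.

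**The SAP never says that improvements create records.** True, but it refers to each change in grade without limiting this to worsening.

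**An over-inclusive rule is defensible for descriptive safety.** It answers an openly stated data limitation, and no formal safety tests are planned. This has force and is why the fix keeps unlinkable records. It is not simply cautious, however: similar carry-over in both arms pulls a risk ratio towards 1.

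**The tables count patients, and pre-treatment events are tabulated separately.** Counting patients removes repeats within a period. It does not help when a man's only record of that term in the period is a carried-over grade change.

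**Conclusion.** The point holds for the double-blind tables on a literal reading. Both SAPs allow a pre-dose event that only improves to become a TEAE, the protocol's definition does not, and no supplied text adds a worsening condition. For the crossover column it holds only if records are assigned to periods by their own start date.

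The size is unknown. A reader might assume 1 to 2 ongoing events per man at the switch, 10 to 30% of them changing grade and half of those downwards, and so reach 100 × (1 to 2) × (0.10 to 0.30) × 0.5 = 5 to 30 events per 100 crossover men. The documents support none of those inputs. The result also counts events rather than patients; events can cluster in the same men, and a man with another open-label TEAE adds nothing to the count of men with any TEAE.

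The double-blind effect is probably small, given the short window between consent and first dose. The crossover column feeds descriptive frequencies only: Supplement 7 limits risk differences, risk ratios, interval-specific incidence and prevalence to the double-blind period. No efficacy conclusion is touched. The change is worth making because it is cheap and removes a disagreement between protocol and SAP, and it matters most for the crossover column.

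**What to change.** In SAP v4.2 section 6.5.2 and Supplement 7 section 6.5.2:

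1. Link grade records by patient, preferred term and adjoining dates.
2. Count a linked record as treatment-emergent in a period only if the event is new in that period or its grade exceeds the last grade before that period's first dose. For crossover men, this is the first open-label dose. Use the last grade, not the highest: an event at grade 3 on placebo that settles to grade 1 before the switch and returns to grade 3 on darolutamide should count.
3. Keep any record that cannot be linked as a TEAE.
4. State in Supplement 7 how events ongoing at the switch are assigned.
5. Reconcile the definition with protocol section 7.8.1, noting that a pure onset rule misses true worsening.

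The cost is a short rule in each document and a linking step in the adverse event derivation. The downside is real. Linkage is imperfect, as the SAP itself warns for grade records, and a distinct new event with the same preferred term and adjoining dates could be merged into an older one. The current record-based count should therefore be shown as a supporting table.
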